***Hypothesis tests for B-study are as follows:***

The first set of hypotheses to be tested in B-study (the third set of hypotheses for the study as a whole) is as follows:

- $H_{03}: \mu^{(\text{ADAS-cog, azeliragon, B-study})} = \mu^{(\text{ADAS-cog, P, B-study})}$
- $H_{13}: \mu^{(\text{ADAS-cog, azeliragon, B-study})} \neq \mu^{(\text{ADAS-cog, P, B-study})}$ ,

where  $\mu^{(\text{ADAS-cog, azeliragon, B-study})}$  and  $\mu^{(\text{ADAS-cog, P, B-study})}$  denote the true mean changes from Baseline at Month 18 on the ADAS-cog total score for the B-study azeliragon 5 mg/day added to SoC and placebo added to SoC groups, respectively.

The second set of hypotheses to be tested in B-study (the fourth set of hypotheses for the study as a whole) is as follows:

- $H_{04}: \mu^{(\text{CDR-sb, azeliragon, B-study})} = \mu^{(\text{CDR-sb, P, B-study})}$
- $H_{14}: \mu^{(\text{CDR-sb, azeliragon, B-study})} \neq \mu^{(\text{CDR-sb, P, B-study})}$ .

where  $\mu^{(\text{CDR-sb, azeliragon, B-study})}$  and  $\mu^{(\text{CDR-sb, P, B-study})}$  denote the true mean changes from Baseline at Month 18 on the CDR-sb score for the B-study azeliragon 5 mg/day and placebo groups, respectively.

**STAGE 2:**

If and only if both hypothesis tests in A-study AD subjects and also B-study AD subjects for both co-primary variables (ADAS-cog and CDR-sb) have  $p < 0.05$  (i.e.,  $p < 0.05$  for ADAS-cog demonstrating statistical superiority of azeliragon 5 mg added to SoC versus placebo added to SoC and also  $p < 0.05$  for CDR-sb demonstrating statistical superiority of azeliragon 5 mg added to SoC versus placebo added to SoC (i.e., statistical significance of the test of the null hypothesis for each A-study and B-study independently), testing will proceed to the fifth set of hypotheses to the expansion of the population of subjects from A-study and B-study combined.

Consistent with the FDA draft Guidance for Industry: *Alzheimer's Disease: Developing Drugs for the Treatment of Early Stage Disease* (February, 2012), toward the goal of demonstrating disease modification, analysis of MRI data (hippocampal volume as the key secondary endpoint) will be done conditional on significance of the above-named hypothesis tests:

The next set of hypotheses to be tested is as follows:

- $H_{05}: \mu^{(MRI, \text{azeliragon, All})} = \mu^{(MRI, P, All)}$
- $H_{15}: \mu^{(MRI, \text{azeliragon, All})} \neq \mu^{(MRI, P, All)}$

where  $\mu^{(MRI, \text{azeliragon, All})}$  and  $\mu^{(MRI, P, All)}$  denote the true mean changes from Baseline at Month 18 on MRI volume measures for all AD azeliragon 5 mg/day and placebo groups, respectively.

### STAGE 3:

If all hypotheses defined in both Stage 1 and Stage 2 demonstrate statistical superiority of azeliragon TTP488 5 mg added to SoC versus placebo added to SoC, the secondary efficacy endpoints will be tested in hierarchical order. The order of testing is defined in [Section 4.1](#) (efficacy variables). The outline of the hierarchical testing is:

- First, the secondary endpoint ranked as #1 will be compared between azeliragon TTP488 5 mg added to SoC versus placebo added to SoC in the study as a whole (study A and study B combined). If  $p < 0.05$ , statistical significance will be declared.
- Secondly, if the secondary endpoint ranked as #1 showed a statistically significant difference, the secondary endpoint ranked as #2 will be compared between azeliragon 5 mg added to SoC versus placebo added to SoC in the study as a whole (study A and study B combined). If  $p < 0.05$ , statistical significance will be declared.

The hierarchical testing will continue with the consecutive secondary endpoints, as long as the previous secondary endpoint is declared as statistically significant.

### 3 Populations of Analysis

In accordance with guidance from the International Conference of Harmonization of Technical Requirements for Registration of Pharmaceuticals for Human Use (ICH) guideline ICH E9 Statistical Principles for Clinical Trials (1998), the following data sets will be used for all statistical analysis:

- The full analysis set (FAS) includes all randomized subjects who receive any study medication and have at least one post-Baseline.
- The per protocol set (PPS) includes all subjects in the FAS who receive at least 6 months of study drug and attend at least 6 scheduled visits, except for those who are excluded because of major protocol violations, where a major protocol violation is one that may affect the interpretation of study results (e.g., non-compliance with study medication requirements as evaluated using TTP488 plasma concentration below the limit of quantification at last study visit during 18-month treatment period). The intended criterion of “6 scheduled visits” includes screening and baseline and at least 4 scheduled clinic visits after first dose of study medication.

Final determinations of the PPS will be made at the masked data review meeting (BDRM) held in accordance with ICH E9 prior to the lock data. The complete specification (made blinded to treatment arm) will be documented in the minutes to the blind data review meeting held prior to lock the data.

- The safety set (SAF) includes all subjects who receive any study medication.

For the purpose of understanding the influence of dropouts on study conclusions, the FAS will be partitioned into subjects who complete (completers) and subjects who do not complete (dropouts). For purposes of this study, a subject is a completer if the subject has received treatment for 18 months and has efficacy data for 18 months (evaluation is made at the endpoint level, so if a subject is missing ADAS-cog at Month 18 but has CDR-sb at Month 18, this subject is included in analyses for which the data are available).

It is noted that if the FAS and PPS do not differ by more than 15% in numbers of individuals, analysis may be limited to the FAS (ITT analysis), and the PP analysis will not be conducted.

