9.13 INTERIM ANALYSIS

Except for the ongoing, blinded medical monitoring of accruing data and except for the ongoing review by the IDMC, no interim analysis is planned for this study.

As a conservative measure, an alpha adjustment is applied to accommodate up to 10 analyses by the IDMC. Alpha = 0.0001 is apportioned to each of no more than 10 analyses by the IDMC.

With the exception of the IDMC, no unblinding is planned in this study for any reason other than emergency unblinding for medical imperatives.

It is emphasized that there is no interim analysis in this study for efficacy. The interim analyses described in this section refer to the analyses done by the IDMC for safety monitoring only.

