- To guide the analysis and reporting of study results to enable the production of valid and accurate depictions of study data.

The approach will conform to FDA guidance as described in *Guidance for Industry Statistical Principles for Clinical Trials* ([1998](#)).

This final draft SAP reflects finalization of all attributes of the analysis plan that pertain to or affect alpha and key estimation activities, including initial feedback from the FDA. In accordance with ICH E9, the SAP was finalized prior to any unblinding, and following the final blind data review meeting (BDRM) when the per-protocol set (PPS) was characterized. The

SAP will be updated, if warranted, based on future feedback from FDA reviewers; any changes to the SAP after finalization will be tracked in amendments similar to the process for the study protocol.

Please note that this SAP describes the statistical analyses of two studies with a common infrastructure (A-study and B-study). The statistical analysis will be performed independently as two separate studies (the A-study and the B-study) for the co-primary variables: change from baseline in ADAS-cog and change from baseline in CDR-sb. For the key secondary variable (and for all other secondary variables), all study subjects in both the A- and B- studies (A-study and B-study subjects combined) will be used for inferential purposes. All clinical efficacy variables will be summarized statistically for descriptive purposes for A-study and B-study separately (as well as combined). The randomization process supports the independent analysis of the A-study and the B-study, and also supports the statistical analysis of patients from both studies (combined) for the key secondary and other secondary variables. Safety analyses will also be performed on all patients in both studies.

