### 6.2 Missing Data

In general, missing clinical data will not be imputed, except where explicitly defined. In the event of study withdrawal, a subject's final assessment will be used as the endpoint value, if applicable. For Trail Making Test A & B, if the assessment was not done due to cognitive reasons, the max score would be imputed. Note that the reason for "not-done" assessment is captured in the eCRF, and the specify field provides reason why. If the reason relates to cognitive reasons, the maximum time for Trails A (150 seconds) or for Trails B (300 seconds) is used.

Data are considered to be "on-treatment" if the assessment or collection follows the first administration of study medication and if the assessment occurs within 45 days following the final administration of study medication, justified based on the long half-life of this drug.

Dates with missing fields will not have days imputed.

In accordance with the recommendations of the report from the National Academy of Science (NAS) panel "*The Prevention and Treatment of Missing Data in Clinical Trials*," (National Research Council, 2010), sensitivity analyses will be done to ensure that study conclusions are robust against missing data. Last observation carried forward (LOCF) and baseline observation carried forward (BOCF) methods may be used as appropriate in sensitivity analysis. Missing data types will be examined, and statistical methodologies for appropriate sensitivity analyses will be finalized during blind data review as patterns emerge as the study progresses. Primary methodologies following the ITT principle are not subject to change.

The three types of missing data ([Rubin, 1976](#)) are considered to examine robustness of analysis conclusions against missingness and type of missingness:

- MCAR (missing completely at random) assumes the event of missingness is independent both of observable values and of unobservable values, and the missingness is entirely at random.
- MAR (missing at random) assumes that the missingness can be fully accommodated by accounting for variables where data are available.

- MNAR (missing not at random) the missingness may be related to the reason the data are missing.

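### The SAP's example compliance criterion for the per-protocol set (TTP488 below the quantification limit) cannot be applied blind to treatment as written

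*SAP*

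**What the plan says.** SAP 3 builds the PPS from the FAS. A patient needs at least 6 months of study drug and at least 6 scheduled visits, and must have no major protocol violation. The example given of such a violation is "non-compliance with study medication requirements as evaluated using TTP488 plasma concentration below the limit of quantification at last study visit" during the 18-month treatment period. The same section puts the final PPS decisions at the masked data review before lock and adds: "The complete specification (made blinded to treatment arm) will be documented in the minutes to the blind data review meeting".

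Four other places bear on this:

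- Protocol 9.3 gives a different example of a major violation: less than 50% of the prescribed medication taken. SAP 1.9 reports a single modification from the protocol's statistical section, the removal of Bazett's correction, and does not list this change.
- SAP 1 dates its own completion to after the last blind data review, at which the PPS was characterised, and before any unblinding.
- SAP 6.2 says that "statistical methodologies for appropriate sensitivity analyses will be finalized during blind data review as patterns emerge as the study progresses", but also that "Primary methodologies following the ITT principle are not subject to change".
- Protocol 9.13 says: "With the exception of the IDMC, no unblinding is planned in this study", apart from medical emergencies.

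Under SAP 3 and 5.2.1.4, the analyses are repeated on the PPS if it differs from the FAS by more than 15%. Otherwise the PPS analysis may be omitted.

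**The concern.** TTP488 is the study drug, so a measurable level identifies an azeliragon patient and an unmeasurable one very probably a placebo patient. A compliance rule built on that measurement is not neutral between the arms. It fails in one of two ways. Applied to everyone, it treats every placebo patient as non-compliant. Applied sensibly, it needs the treatment code, or results that amount to it, at a meeting described as blind.

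At stake is whether the claim of a blind PPS decision can be verified. Protocol 7.4 and SAP 4.3 and 5.5 cover the sampling and analysis of concentrations but say nothing about who may see results before lock. Elsewhere the protocol does write such barriers: the CDR rater is kept from ADAS-cog data (3.0), the imaging readers are blind to treatment (7.6, 7.8), and individual ApoE results are not released to sites (7.9). No equivalent is stated for the one laboratory result that reveals the arm.

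**Working it through.** The plan states no figure for this criterion, so there is none to reproduce. The check asks how well the measurement separates the arms and what the literal rule does to the PPS.

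**Inputs from the documents**
- 1:1 allocation (SAP 1.4).
- Phase 2 troughs on 5 mg/day, one median per patient, n = 131: mean 13.02, median 12.25, 95% CI of the mean 11.74 to 14.31 (Protocol 1.1.4, Table 2).
- Anticipated concentration on 5 mg/day: 8 to 20 ng/mL across fasted and fed states (Protocol 1.1.4).
- Mean half-life 18 days in elderly participants (Protocol 1.1.3).
- PPS trigger 15% (SAP 3, 5.2.1.4).

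**Assumptions, because the documents give no value**
- Quantification limit L between 0.1 and 2 ng/mL.
- Lognormal troughs.
- A fraction q of azeliragon patients below the limit, 0% to 10%.
- Placebo patients always below the limit, and equal arms in the FAS.

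**Step 1. Is an azeliragon patient who is taking drug ever below the limit?**
- SD = half-width × √n / t = 1.285 × √131 / 1.978 = 7.43.
- Log-SD = √ln(1 + (7.43/13.02)²) = 0.53.
- P(below L) = Φ((ln L − ln 12.25)/0.53). This is 0.0003 at L = 2, about 1 × 10⁻⁶ at L = 1, and below 1 × 10⁻¹⁹ at L = 0.1.

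**Step 2. How long off drug before the level falls below the limit?**
- Days = 18 × log₂(12.25/L): about 47 at L = 2, 65 at L = 1 and 125 at L = 0.1.

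An azeliragon patient is therefore below the limit only after a long interruption.

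**Step 3. What does the result say about the arm, and what does the rule remove?**
- P(placebo given below limit) = 1/(1 + q).
- Share of sampled patients whose arm is inferred correctly = 1 − q/2.
- Share of FAS removed by the literal rule = 0.5 + 0.5q.
- Share removed if limited to azeliragon patients = 0.5q.

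| q | P(placebo given below limit) | Arm inferred correctly | Removed, literal rule | Removed, azeliragon only |
|---|---|---|---|---|
| 0% | 100% | 100% | 50% | 0% |
| 1% | 99.0% | 99.5% | 50.5% | 0.5% |
| 5% | 95.2% | 97.5% | 52.5% | 2.5% |
| 10% | 90.9% | 95.0% | 55% | 5% |

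**Step 4. Does the conclusion need every patient to have a sample?** No. If a share s of placebo patients has a last-visit result, the literal rule removes at least 0.5s of the FAS from that arm. This passes 15% once s exceeds 0.15/0.5 = 30%. At the planned 20% dropout, even if only completers had a sample, it would be 0.5 × 0.8 = 40%.

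The literal rule thus triggers the PPS analysis by itself and, where all are sampled, leaves it without a placebo group. The azeliragon-only version stays under 15% on its own, but it draws every exclusion from one arm and can be applied only by someone who knows the arm.

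**The case against.** The strongest reply is that the documents assert blinding, and nothing in them says that patient-level concentrations were put before the review. A party outside the review could apply the rule and return a short list of non-compliant patients. Or the meeting could settle a specification to be programmed later, which is a possible reading of "The complete specification (made blinded to treatment arm) will be documented in the minutes". This stands against one tempting inference, that the review was in fact unblinded. The documents do not support it: silence about a safeguard is not evidence that results were seen, and the minutes are not available. It does not rescue the text, because neither arrangement is written down, no unblinded adjudicator is provided for, and the rule does not say that it applies to azeliragon patients only.

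The second reply is that the criterion is one example, beside duration and visit criteria that do not reveal the arm, and that the PPS is supportive and may never be analysed. This also stands and limits the importance of the point.

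A reader might further infer that the sensitivity analyses and final SAP text were chosen with arm and outcomes in view. The documents do not support that either. SAP 6.2 describes finalisation during blind review as a process, without tying it to the meeting on the PPS, and no section says outcome data were shown there. The primary methods are declared fixed. SAP 5.2.1 already sets out multiple imputation under missing at random, the tipping-point steps, the copy-reference analysis and the LOCF ANCOVA. What stays open is narrower: SAP 6.2 leaves LOCF and baseline-carried-forward use to judgement, and SAP 5.2.1 allows unplanned sensitivity analyses.

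Finally, a count of the patients whose arm could be inferred would measure potential disclosure. It would not measure bias in any estimate.

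**Conclusion.** The point holds in limited form and should be corrected. As written, the concentration example in SAP 3 cannot be applied by anyone blind to arm. Taken literally, it excludes the placebo arm, about half of the FAS and well over the 15% trigger. Restricted to azeliragon patients, it needs the arm. No stated safeguard closes the gap.

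That placebo patients cannot have measurable drug is enough for the contradiction, and the 1:1 allocation gives its size. The finer figures (arm inferred correctly for 95% to 99.5% of sampled patients at q = 10% to 1%) rest on the assumed q. The claim that patients on drug are almost never below the limit rests on the assumed quantification limit and lognormal shape.

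The exposure is confined to the supportive PPS, the decision whether to run it, and the sensitivity choices left open at blind review. The primary MMRM on the FAS is not affected, and actual unblinding is not shown.

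**What to change.** - **SAP 3, pre-lock exclusion.** Replace the concentration example with an arm-neutral measure already collected: the capsule counts of Protocol 5.3.3, with the Protocol 9.3 example of less than 50% of prescribed medication taken.
- **SAP 3, access.** State that TTP488 and metabolite results are withheld from the study team and the blind review until the relevant sub-study is locked and unblinded. Tying this to each sub-study respects Protocol 11.1, which has the sub-studies locked and reported separately, so A-study reporting need not wait for B-study.
- **Concentration-based set, if wanted.** Pre-specify the numeric limit and the visit, define the rule for azeliragon patients, and apply it by program after lock as a separate supportive set. State that its exclusions come from one arm only.
- **SAP 1.9.** List the change from the Protocol 9.3 example.
- **Disclosure.** If concentrations were seen at the review, say so in the SAP and the clinical study report.

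The cost is SAP wording and a restriction on data transfer, with no new procedures. The downside is that concentration-based compliance is known only after lock.

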## 4 Variables of Analysis

### 4.1 Efficacy Variables

Efficacy evaluation will include the co-primary endpoints (ADAS-cog and CDR-sb), key secondary measures, and other efficacy markers.

#### 4.1.1 Primary Efficacy Variable

The primary analysis will include assessment of the following variables of analysis.

- Mean change from Baseline to Month 18 in ADAS-cog
- Mean change from Baseline to Month 18 in CDR-sb.

Key supportive variables will include mean change from Baseline to all other Visits in ADAS-cog and mean change from Baseline to all other Visits in CDR-sb. Time to threshold worsening will be done as supportive analyses for change in ADAS-cog with thresholds of 7 points as an indicator of progression, with other cut-points from 1 to 20 as exploratory.

#### 4.1.2 Key Secondary Variables of Analysis (Imaging)

The key secondary endpoint is:

- Change from Baseline in hippocampal volume at Month 18.

PET variables are considered to be exploratory and will be defined separately.

#### 4.1.3 Secondary Variables

The following secondary efficacy endpoints will be evaluated in hierarchical order:

- Secondary endpoint ranked as #1: The change from baseline to final visit in the ADCS-ADL scale through Month 18.
- Secondary endpoint ranked as #2: Change from Baseline in the Neuropsychiatric Inventory (NPI) total score at Month 18.
- Secondary endpoint ranked as #3: The change from baseline to final visit in the Mini-Mental State Examination (MMSE) through Month 18.
- Secondary endpoint ranked as #4: Change from Baseline on the Trail Making Test Version A time at Month 18.
- Secondary endpoint ranked as #5: Change from Baseline on the Trail Making Test Version B time at Month 18.
- Secondary endpoint ranked as #6: Change from Baseline on the Continuous Oral Word Association Task (COWAT) score at Month 18.
- Secondary endpoint ranked as #7: Change from Baseline on the Category Fluency Test (CFT) score at Month 18.

- Secondary endpoint ranked as # 8: Change from Baseline in the Dementia Quality of Life (DEMQOL) -Proxy total score at Month 18.

#### **4.1.4 Other Efficacy Variables of Analysis**

Additional efficacy variables of analysis are as follows:

- Responder analysis at Months 3, 6, 9, 12, 15 and 18 based on ADAS-cog (increase from baseline of 7 points or more) and responder analysis at Months 3, 6, 12, and 18 based on the CDR-sb (increase from baseline of 1 point or more). It is noted that a responder is a subject who has not declined, and thresholds are used for classification of having declined.
- Change from Baseline in ventricular volume at Month 18.
- Change from Baseline in whole brain volume at Month 18.
- Time to loss of one global stage on the Clinical Dementia Rating (CDR) score through Month 18.
- Change from Baseline on the ADAS-cog at Months 3, 6, 9, 12 and 15 and at Months 3, 6 and 12 for the CDR-sb and CDR subscale scores.
- Individual item responses on the Resource Utilization in Dementia (RUD) questionnaire and the total caregiver time spent assisting the patient based on the RUD at Months 6, 12, and 18.
- Proportion of participants who enter intermediate or long-term residential care (RUD) at Months 6, 12, and 18.
- Change from Baseline in the Dementia Quality of Life (DEMQOL) - Proxy total score at Months 6 and 12.
- Change from Baseline in the Neuropsychiatric Inventory (NPI) total score and subscale scores at Months 3, 6 and 12.
- Change from Baseline on the Mini-mental State Examination (MMSE) total score at Months 3, 6 and 12.
- Change from Baseline on the Continuous Oral Word Association Task (COWAT) score at Months 3, 6 and 12.
- Change from Baseline on the Category Fluency Test (CFT) score at Months 3, 6 and 12.
- Change from Baseline on the Trail Making Test (Versions A and B) time at Months 3, 6 and 12.

- Change from Baseline in the extent of brain glucose hypometabolism at Month 18.
- Change from Baseline in the severity of brain glucose hypometabolism at Month 18

